1.3. Study Rationale and Dose Selection

1.3.1. Study Rationale

In over half of patients with EGFR-mutant NSCLC acquire resistance to first or second generation TKIs (eg, gefitinib, erlotinib, or afatinib), is associated with the development of the secondary mutation in EGFR exon 20, T790M.¹³ Among the remaining cases, a number of other proposed mechanisms, including the up-regulation of “bypass track” signaling pathways, may be responsible for treatment resistance. AXL expression was observed to be up-regulated in approximately 20% of EGFR-mutant NSCLC patients experiencing disease progression on erlotinib.^{27,28}

Increased expression of AXL has been observed in EGFR-mutant NSCLC tumor biopsies obtained from patients with acquired resistance to TKIs.²⁸ As a member of the mammalian TYRO-3, AXL, and MER (TAM) receptor kinase family (named for its members TYRO3, AXL, and MER), AXL is a cell-surface transmembrane receptor containing regulated kinase activity within its cytoplasmic domain, and plays an important role in signal transduction in normal and malignant cells.^{29,30} Overexpression or ectopic expression of TAM receptors is known to occur in a wide array of human cancers.³¹ GAS6 is the major ligand for these TAM receptor tyrosine kinases and, in particular, is the sole ligand for AXL.²⁹ Its binding to the receptors promotes proliferation, survival, and migration of cancer cells in vitro.^{30,32} Abnormal expression and activation of AXL can provide a survival advantage for certain cancer cells, and inhibition of AXL may enhance sensitivity of cancer cells to cytotoxic agents.³⁰

DS-1205c is a novel, specific, small-molecule inhibitor of the receptor tyrosine kinase AXL, and is being developed by Daiichi Sankyo as an oral antitumor agent. Addition of DS-1205c restores TKI sensitivity in HCC827 (EGFR exon19deletion, T790M-negative) tumor xenograft models. Additionally, inhibition of acquired resistance to gefitinib following the addition of DS-1205c has been demonstrated in non-clinical studies.¹

In summary, DS-1205c is hypothesized to show potential activity in combination with gefitinib in T790M mutation-negative EGFR-mutant NSCLC with a manageable safety profile.

1.3.2. Study Dose Setting

1.3.2.1. DS-1205c Starting Dose

The doses of DS-1205c selected for this study are based on nonclinical data and are expressed in doses of DS-1205a (free base). DS-1205c 200 mg capsules contain equivalent to 200 mg of DS-1205a (free form). Nonclinical data showed that a dose of 1000 mg/kg/day of DS-1205c was the STD₁₀ in the mouse. The human equivalent dose (HED) for 1000 mg/kg, based on allometric scaling by surface area, is approximately 81.3 mg/kg, and using one-tenth of this value gives a dose of 8.1 mg/kg as the

recommended starting dose for the proposed clinical study. The value of 8.1 mg/kg is lower than an alternative starting dose (10.8 mg/kg) calculated using one-sixth of the HED for the HNSTD (200 mg/kg/day in males) in the cynomolgus monkey, and thus is considered to be the appropriate upper bound for a starting dose for clinical study in humans.¹ For a 60 kg human, the 8.1 mg/kg dose becomes 488 mg. Therefore, this study will use a starting dose of 400 mg per day of DS-1205c administered orally in 2 divided doses (200 mg twice daily [BID]).

1.3.2.2. Gefitinib Dosage

In this study, DS-1205c will be administered in combination with gefitinib (Iressa[®]). Open-label commercial supplies of gefitinib (Iressa[®]) will be used and reimbursed by the Sponsor. Gefitinib has been approved (Japan [Standard Commodity Classification Number: 874291], July 2002) for the treatment of patients with unresectable or recurrent NSCLC harboring EGFR mutations at a recommended dose of one 250 mg tablet administered orally once daily (QD).

1.4. Risks and Benefits for Study Subjects

1.4.1. Potential Risks Associated With DS-1205c

No safety information in humans is available.

In nonclinical toxicity studies conducted in mice, elevations in clinical laboratories including ALT, AST, ALP GLDH, creatinine kinase (CK), and LDH. In cynomolgus monkeys, DS-1205c-related histopathological findings were observed in the heart, stomach, duodenum, pancreas, lymphoid organs, and liver. In other clinical pathology parameters, prematurely-sacrificed animals showed increases in white blood cell, neutrophil, lymphocyte, monocyte, eosinophil, basophil, and large unstained cell, and increases in ALT, AST, GLDH, LDH, CK, and triglycerides.

1.4.2. Potential Risks Associated With Gefitinib

Refer to the gefitinib package insert for detailed description of potential risks associated with gefitinib. As for potential risks overlapping with DS-1205c, hepatotoxicity has been reported with gefitinib. In subjects who received gefitinib in clinical trials with gefitinib,³³ 11.4% of subjects had increased ALT, 7.9% of subjects had increased AST, and 2.7% of subjects had increased bilirubin. Grade 3 or higher liver test abnormalities occurred in 5.1% (ALT), 3.0% (AST), and 0.7% (bilirubin) of those subjects. The incidence of fatal hepatotoxicity was 0.04%.

1.4.3. Pharmacokinetic Drug Interaction

In vitro metabolism studies using human hepatocytes indicated that major route of metabolism was *N*-glucuronidation. The primary UGT isoform responsible for glucuronidation of DS-1205a was suggested to be UGT1A4, and the second UGT1A1. In a study using microsomes containing recombinant human CYP isoforms, CYP3A4 was the main isoform and CYP3A5 was the minor isoform for the oxidation of DS-1205a.

DS-1205a did not show reversible inhibition of CYP1A2, CYP2B6, CYP2C8, CYP2C9, CYP2C19, CYP2D6, or CYP3A4, and DS-1205a did not show time-dependent inhibition of any CYP isoforms tested. In another in vitro study, DS-1205a had no induction effect on mRNA expression levels or specific enzyme activities of CYP3A4, CYP1A2, or CYP2B6.

In a study using Caco-2 cells, DS-1205a inhibited P-glycoprotein (P-gp)-mediated digoxin transport in vitro, with an IC_{50} of 1.20 μ M. The clinical relevance of this inhibitory effect will depend on the intestinal and systemic concentration that DS-1205a will reach at the therapeutic dose, and on the concomitant drugs in target population.

1.4.3.1. Evaluation of the Potential for PK Interaction Effect on Gefitinib by DS-1205c

Gefitinib is extensively metabolized mainly via CYP3A4 and partially via CYP2D6.³⁴ However, since in vitro assessment shows that DS-1205c is neither an inhibitor nor an inducer of major CYP isoforms, the PK of gefitinib is unlikely to be significantly affected by co-administration of DS-1205c in humans. Although DS-1205c is an in vitro inhibitor of P-gp and gefitinib is an in vitro P-gp substrate, it is not expected that such inhibition will meaningfully impact the PK of gefitinib, given its high absorption and extensive metabolism. Based on mass balance study results of gefitinib, 80.8% of radioactivity was recovered in feces and 3.6% of radioactivity was recovered in urine. Only 4% of the dose recovered in feces was unchanged gefitinib following oral administration of [¹⁴C]-gefitinib.³⁴

1.4.3.2. Evaluation of the Potential for PK Interaction Effect on DS-1205c by Gefitinib

In vitro assessment using human hepatocytes showed that the major metabolic route of DS-1205a was *N*-glucuronidation, and oxidation metabolism was a minor route. The primary UGT isoform responsible for glucuronidation of DS-1205a was suggested to be UGT1A4, followed by UGT1A1, by in vitro studies. It is reported that gefitinib is unlikely to cause clinically significant DDI through inhibition of glucuronidation although gefitinib showed inhibition against UGT1A1, UGT1A7, UGT1A9, and UGT2B7 in vitro,³⁵ it is unlikely for gefitinib to cause clinically relevant increases in the exposure of DS-1205a given that *N*-glucuronidation of DS-1205a is primarily catalyzed by UGT1A4. Gefitinib is a CYP2D6 inhibitor in vivo, and it also inhibits CYP2C19 in vitro.³⁴ The oxidation metabolism of DS-1205a is catalyzed by CYP3A4 and CYP3A5, but not by CYP2C19 or CYP2D6. Therefore, co-administration of gefitinib is not expected to cause clinically significant effects on the PK of DS-1205c via UGT and CYP-related metabolism.

1.4.4. Potential Benefit Associated with DS-1205c

No efficacy information in humans is available.

Nonclinical studies have demonstrated the anti-tumor activity of DS-1205 in combination with gefitinib in xenograft models.¹ Based on the above rationale, and the nonclinical

data, DS-1205c in combination with gefitinib is hypothesized to show activity in EGFR-mutant NSCLC.

2. STUDY OBJECTIVES AND HYPOTHESIS

2.1. Study Objectives

2.1.1. Dose Escalation

Primary Objective

- To assess the safety and tolerability and to determine the recommended dose for expansion (RDE) of DS-1205c when combined with gefitinib in metastatic or unresectable EGFR-mutant NSCLC subjects who are T790M mutation-negative after disease progression during treatment with gefitinib, erlotinib, afatinib, dacomitinib, or osimertinib

Secondary Objectives

- To characterize the PK of DS-1205a (free form of DS-1205c) when DS-1205c is administered alone; and of DS-1205a and gefitinib when DS-1205c is administered in combination with gefitinib
- To investigate the antitumor activity of DS-1205c in combination with gefitinib

Exploratory Objectives

- To evaluate the effect on QTc when DS-1205c is administered alone or in combination with gefitinib
- To identify biomarkers that correlate with efficacy or toxicity to DS-1205c in combination with gefitinib
- To assess changes in the profile of EGFR mutations and/or other genes in cell-free DNA (cfDNA) during treatment with DS-1205c in combination with gefitinib
- To conduct metabolite analysis of DS-1205c

2.1.2.

CCI

CCI

2.2. Study Hypothesis

2.2.1. Dose Escalation

DS-1205c in combination with gefitinib will be safe and well tolerated in metastatic or unresectable EGFR-mutant NSCLC subjects who are T790M mutation-negative, after disease progression during treatment with gefitinib, erlotinib, afatinib, dacomitinib, or osimertinib.

2.2.2. CCI

2.3. Study Endpoints

2.3.1. Dose Escalation

Primary Endpoints (ie, Primary Outcome Measures)

- To determine the safety and tolerability of DS-1205c in combination with gefitinib, the endpoints will include dose-limiting toxicities (DLTs), serious adverse events (SAEs), treatment-emergent adverse events (TEAEs), physical examination findings (including Eastern Cooperative Oncology Group [ECOG] performance status [PS]), vital sign measurements, ophthalmologic findings, standard clinical laboratory parameters, ECG parameters (including the change-from-baseline ECG parameters: HR; PR; QTcF; and QRS intervals [Δ HR, Δ PR, Δ QTcF, and Δ QRS]), echocardiogram (ECHO)/multigated acquisition (MUGA) scan findings, and radiographic findings. AEs and laboratory findings will be graded according to the National Cancer Institute-Common Terminology Criteria for Adverse Events (NCI-CTCAE) version 5.0.

Secondary Endpoints (ie, Secondary Outcome Measures)

- Cycle 0: To assess PK of DS-1205a, the endpoints will include plasma concentration of DS-1205a versus time, and Cmax, Tmax, trough plasma concentration (Ctrough), area under the plasma concentration-time curve during a dosing interval (AUCtau), and other PK parameters, as appropriate.

- Cycle 1 and beyond: To assess the PK of DS-1205a, and gefitinib, the endpoints will include plasma concentration of DS-1205a, and gefitinib versus time, and maximum observed analyte concentration during a dosing interval (Tau) (Cmax), Tmax, Ctrough, AU τ , and other PK parameters, as appropriate.
- The efficacy endpoint is ORR: the number of subjects with best objective response (complete response [CR] or PR, divided by the number of subjects in the analysis population), as determined by Investigator assessment based on RECIST version 1.1. Additional efficacy endpoints are DOR (the time from documentation of tumor response [either CR or PR] to disease progression), disease control rate (DCR) (the sum of CR rate, PR rate, and stable disease [SD] rate), PFS, time to response (TTR); and OS.

Exploratory Endpoints (ie, Exploratory Outcome Measures)

- Biomarkers measured in tumor specimens that correlate with response or toxicity to DS-1205c in combination with gefitinib (eg, AXL immunohistochemistry [IHC], AXL and AXL pathway genes measured by NanoString multiplex RNA and/or other methods, and/or protein analysis) will be assessed.
- Biomarkers measured in plasma that correlate with response or toxicity to DS-1205c in combination with gefitinib (eg, cfDNA) will be assessed.
- EGFR mutation(s) or mutations in other genes in cfDNA during treatment with DS-1205c in combination with gefitinib will be assessed.
- To assess change-from-baseline QTcF (Δ QTcF) when DS-1205c is administered alone or in combination with gefitinib.

2.3.2:

CCI

Figure 1 consists of three vertically stacked bar charts. Each chart has 'Age Group' on the x-axis (18-44, 45-64, 65+) and 'Type of Cancer' on the y-axis (Lung, Breast, Colorectal, Prostate, Melanoma, Other). The bars represent the percentage of patients for each cancer type within each age group. The top chart is for Lung cancer, the middle for Breast cancer, and the bottom for Colorectal cancer.

Age Group	Lung (%)	Breast (%)	Colorectal (%)
18-44	10	10	10
45-64	25	25	25
65+	35	35	35

CCI

[figure not shown]

3. STUDY DESIGN

[figure not shown]
3.1. Overall Design Summary

This is a multi-center, open-label Phase 1 study of DS-1205c in combination with gefitinib in subjects ≥ 20 years old who have metastatic or unresectable EGFR-mutant NSCLC and are T790M mutation-negative after disease progression during treatment with gefitinib, erlotinib, afatinib, dacomitinib, or osimertinib. This study includes two parts: Dose Escalation and Dose Expansion.

Figure 3.1: Study Schema: Dose Escalation

C = Cycle

3.2. Treatment Groups

In Dose Escalation, subjects will receive DS-1205c at varying doses based on their assigned cohort (see [Table 3.1](#)). In Dose Expansion, all subjects will receive the RDE dose as a single cohort.

3.2.1. Dose Escalation

3.2.1.1. Cycle 0 (Monotherapy, 7 Days)

To minimize the possibility of developing tumor flare with discontinuation of EGFR TKI, subjects who fulfill eligibility criteria will be instructed to continue their current EGFR TKI (gefitinib, erlotinib, afatinib, dacomitinib, or osimertinib) during screening. The last dose of gefitinib, erlotinib, afatinib, dacomitinib, or osimertinib must be taken 1 day before breakfast in clinic on Cycle 0, Day 1, as depicted in [Figure 3.1](#) above. This schedule provides an 8-day window between the last dose of gefitinib, erlotinib, afatinib, dacomitinib, or osimertinib, and the first dose of gefitinib.

Once eligibility is confirmed, subjects will be assigned by the Sponsor to receive DS-1205c at a specific dose level ([Table 3.1](#)). This will be either the current escalation dose (as determined by an algorithm described in detail in Section [3.2.1.2](#) below) or a previously assigned lower dose (ie, cohort backfilling).

Table 3.1: Dose Escalation Provisional Cohorts and Provisional Dosages

Cohort ^a	Cycle 0 Monotherapy (7-day cycle)	Cycle 1 and Beyond Combination Therapy (21-day cycles)	
	DS-1205c Dosage ^b	DS-1205c Dosage ^b	Gefitinib Dosage ^c
1	200 mg BID	200 mg BID	250 mg QD
2	400 mg BID	400 mg BID	250 mg QD
3	600 mg BID	600 mg BID	250 mg QD
4	800 mg BID	800 mg BID	250 mg QD

BID = twice daily; mg = milligrams; QD = once daily

- a. The second subject in each cohort should start dosing at least 24 hours after the initial dosing of the first subject. The cohort numbers in this table do not denote actual order of dose transition on the trial.
- b. Administer with a meal, with 240 mL of water. On the morning of Endpoint ECG days, breakfast should be started 30 minutes prior to dosing and should be completed within approximately 20 minutes. For all other dosings, it is recommended that meals (breakfast or dinner) be completed within approximately 30 minutes; DS-1205c should be taken immediately after meal completion. Doses of DS-1205c should be taken approximately 12 hours apart.
- c. Co-administer with morning dose of DS-1205c.

Subjects will report to the clinic on Day 1 before Cycle 0 to obtain ECGs at specified time points outlined in the Schedule of Events, Dose Escalation (Cycle 0) (see [Table 6.1](#)). These time points will be time matched to ECGs obtained on Cycle 0, Day 1.

Beginning with Cycle 0, Day 1, subjects will receive DS-1205c BID for 7 days. DS-1205c should be taken with a meal. On the morning of Endpoint ECG days, breakfast should be started 30 minutes prior to dosing and should be completed within approximately 20 minutes. For all other dosings, it is recommended that meals (breakfast or dinner) be completed within approximately 30 minutes; DS-1205c should be taken immediately after meal completion. Time-matched ECGs will be obtained and blood samples for PK will be collected at specified time points ([Table 6.1](#)). Additional safety,

PK, and ECG assessments will be performed/obtained on specific days and time points over the 7-day run-in period (Section [6.1.2](#)).

3.2.1.2. Cycle 1 and Beyond (Combination Therapy)

In Cycle 1 and beyond, DS-1205c will be taken BID in combination with 250 mg QD of gefitinib in 21-day cycles, as outlined in detail in the Schedule of Events, Dose Escalation, (Cycle 1 and Beyond) ([Table 6.2](#)).

Dose escalation of DS-1205c to determine the RDE will be guided by the modified Continuous Reassessment Method (mCRM) using a Bayesian logistic regression model (BLRM) following the escalation with overdose control (EWOC) principle (Section [11.11](#)). The logistic regression model for the dose-response (DLT rate) relationships will include 2 parameters: the intercept and slope. The DLT-evaluation period is defined as the 7 days of Cycle 0 plus the 21 days of Cycle 1 (28 days total). A DLT-evaluable subject is defined as a subject who has received DS-1205c and either has completed minimum safety evaluation requirements over the DLT-evaluation period or has experienced a DLT during the DLT-evaluation period. After at least 3 DLT-evaluable subjects of each cohort complete DLT evaluation, posterior distributions of DLT rate will be derived for all dose levels based on the BLM using DLT outcome data from all assessed doses and a pre-specified prior distribution for the model parameters. The EWOC principle requires that the mCRM-recommended dose for the next cohort of subjects is the one with the highest posterior probability of the DLT rate in the target DLT rate interval with the overdose control constraint for excessive or unacceptable toxicity.

As an exception, the model will be reevaluated before enrollment of any additional subjects to the cohort if 2 DLT-evaluable subjects in the cohort experience DLT before the enrollment of the third subject. Enrollment of subjects to a new higher-dose cohort requires completion of DLT evaluation of at least 3 subjects treated in the current cohort. Subjects who have neither completed DLT evaluation nor experienced DLT will not be included in a BLM update. In the event when subjects in the previous cohort experience DLTs after enrollment of subjects to a new cohort has begun, dose level assignment of the next subject in the new cohort will be based on an updated BLM using DLT outcome data from all assessed doses. Subjects already receiving treatment will continue treatment at their assigned dose level or per dosing modification guidelines outlined in Section [5.4](#).

Subjects can be backfilled (added) to lower doses previously proven to be safe at any point during Dose Escalation. Lower or intermediate dose levels may also be considered based on review of available safety, tolerability, and PK data in this and other studies with the investigational agent. There will be no intrasubject dose escalation.

Any dose cohort may be expanded to include additional subjects for further evaluation of safety or PK parameters as required. The dose level for next cohort will be chosen by the Sponsor as outlined in Section [11.11.3](#) based on the dose recommendation by the mCRM, clinical assessment of TEAEs, toxicity profiles, efficacy, PK, and PD information observed thus far.

The number of treatment cycles is not fixed. Subjects may continue study treatment until PD, unacceptable toxicity, withdrawal of consent, or other reasons detailed in Section 5.6.1.

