5. STUDY TREATMENT(S)

5.1. Assigning Subjects to Treatments and Blinding

5.1.1. Treatment Group(s)/Sequence(s)

This study is an open-label, non-randomized study. DS-1205c will be administered orally at a starting dose level of 200 mg BID in combination with a fixed dose of 250 mg gefitinib administered orally QD in cycles of 21 days, except for Cycle 0 of Dose Escalation, where DS-1205c will be administered BID as monotherapy. Additional dose levels of DS-1205c may be tested based on the emerging data from Dose Escalation and the proposed lower doses.

In Dose Escalation, each dose cohort is planned to include at least three subjects. Subjects are assigned to dose cohorts by the Sponsor as detailed in Section [3.2.1.2](#) above. For additional safety, the second subject in each dose cohort should start dosing at least 24 hours after the initial dosing of the first subject.

[figure not shown]
CCI

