11.11.3. Escalation With Overdose Control Principle

Dose recommendation for the next cohort of patients will be based on summaries of the posterior probability of DLT rate for provisional doses.⁴⁴ After each cohort of subjects completes DLT evaluation during Cycle 1, the joint posterior distribution of the BLRM parameters will be generated according to the Bayes' theorem based on the likelihood function of the accumulated DLT data from Cycle 1 and the prior distribution. Posterior probabilities of DLT rate at different dose levels will then be obtained from updated BLRM, and summarized for DLT rate in 4 different ranges: under-dosing (ie, DLT rate within [0, 0.16]), target toxicity (ie, DLT rate within [0.16, 0.33]), excessive toxicity (ie, DLT rate within [0.33, 0.60]), and unacceptable toxicity (ie, DLT rate within [0.60, 1.00]). The dose level recommended by mCRM for dosing next cohort will be based on these probabilities according to the EWOC principle. The EWOC principle requires that the mCRM recommended dose for the next cohort of subjects is the one with the highest posterior probability of the DLT rate in the target DLT rate range of [0.16, 0.33] among all doses fulfilling the overdose control constraint that there is less than 0.25 of probability for DLT rate > 0.33 (probability for excessive or unacceptable toxicity).

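### Once a third subject is enrolled, nothing obliges a model rerun after a second DLT before another subject joins the same dose

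*Combined protocol and SAP*

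**What the plan says.** Section 3.2.1.2 sets the routine update: "After at least 3 DLT-evaluable subjects of each cohort complete DLT evaluation, posterior distributions of DLT rate will be derived for all dose levels". The evaluation period is 28 days (7 in Cycle 0, 21 in Cycle 1). Section 11.11.3 also ties the update to a cohort completing evaluation.

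Section 3.2.1.2 gives one exception for the cohort being enrolled. The model is rerun before anyone else is added "if 2 DLT-evaluable subjects in the cohort experience DLT before the enrollment of the third subject". The other DLT-driven update looks back at an earlier cohort: "In the event when subjects in the previous cohort experience DLTs after enrollment of subjects to a new cohort has begun", the next assignment in the new cohort uses an updated model. Pending subjects are left out: "Subjects who have neither completed DLT evaluation nor experienced DLT will not be included in a BLM update".

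On cohort size and pace:
- Section 5.1.1 plans at least three subjects per cohort and states no maximum.
- Section 3.2.1.2 adds: "Any dose cohort may be expanded to include additional subjects for further evaluation of safety or PK parameters as required".
- The only stagger, in Section 5.1.1 and in footnote a of Table 3.1, is that "the second subject in each dose cohort should start dosing at least 24 hours after the initial dosing of the first subject".

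Section 11.11.3 restricts the recommended dose for the next cohort by an "overdose control constraint that there is less than 0.25 of probability for DLT rate" above 0.33. Section 3.2.1.4 has DLTs communicated to the Sponsor in real time and safety review meetings held as needed. It names no DLT count and no enrolment hold.

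**The concern.** The exception shows that the authors regard two DLTs in a cohort as reason to consult the model before enrolling anyone else. Yet it depends on when the third subject was enrolled, which says nothing about the toxicity of the dose. If subjects 1 and 2 have DLTs the day before subject 3 is enrolled, a rerun is mandatory. If they have them the day after, it is not.

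A further subject could then start a dose that the plan's own model, if rerun, would exclude. There are two routes:
- the cohort is expanded;
- one of the first three proves non-evaluable (Section 3.2.1.3 excludes subjects who miss more than 25% of doses for reasons unrelated to adverse events), so the three-subject condition for the routine update is unmet.

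The protocol reports no clinical data for DS-1205c (Section 1.1.3) and has no data monitoring committee (Sections 11.8 and 15.9), so the written enrolment rule carries more weight than usual.

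**Working it through.** **Inputs.** Sections 11.11.1 and 11.11.2 give logit π(d) = log α + β·log(d/800). The prior for (log α, log β) is bivariate normal with means −1.1493 and −0.5514, SDs 2.0739 and 1.5228, and correlation −0.1943. I take d as mg per administration, because Section 11.11.2 calls 200 mg the starting dose. The limit is P(π > 0.33) < 0.25 (Section 11.11.3). The posterior is proportional to prior × ∏ π(d)^x·(1 − π(d))^(n − x), for x DLTs in n subjects at each dose, integrated on a 1201 × 1201 grid.

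**Reproducing the plan.** The prior medians come out at 8.0% at 200 mg and 24.1% at 800 mg. Section 11.11.2 states approximately 8% and 24.5%.

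**What the model says after two DLTs.** P(π > 0.33) at the current dose, assuming 0/3 at each lower listed dose:

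| DLTs / subjects | 200 mg | 400 mg | 600 mg | 800 mg |
|---|---|---|---|---|
| 2/2 | 0.92 | 0.62 | 0.50 | 0.62 |
| 2/3 | 0.79 | 0.49 | 0.38 | 0.46 |
| 2/4 | 0.65 | 0.38 | 0.29 | 0.34 |
| 2/5 | 0.52 | 0.30 | 0.22 | 0.246 |
| 2/6 | 0.40 | 0.22 | 0.16 | 0.18 |
| 2/9 | 0.17 | 0.09 | 0.07 | 0.07 |

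Two DLTs with the third subject pending enter as 2/2, because pending subjects are excluded. Every level exceeds 0.25 for 2/2, 2/3 and 2/4. For 2/5 only 200 and 400 mg do; for 2/9 none does.

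**Sensitivity.** With 0/6 at each lower dose, 2/2 (lowest 0.36) and 2/3 (lowest 0.26) still exceed the limit everywhere, but 2/4 does not at 400 mg (0.24) or 600 mg (0.19). If d were total daily dose against the same reference, 2/2 and 2/3 would exceed it everywhere (lowest 0.49 with 0/3 below, 0.39 with 0/6).

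**How often the exception fires.** The documents give neither spacing nor DLT timing. Assume even spacing of g days, DLT time uniform over 28 days, dosing at enrolment, and a true DLT rate p of 0.33 or 0.50. The exception needs subject 1's DLT within 2g days of starting and subject 2's within g days. Among cohorts with at least two DLTs in the first three, the share in which it fires is

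p²·min(1, 2g/28)·min(1, g/28) / [3p²(1 − p) + p³].

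At g = 20 and p = 0.33 this is 0.1089 × 1 × 0.714 / 0.2548 = 0.31. The planned average is 365/18 ≈ 20 days per subject (18 subjects, about 12 months). The last column is simulated: mean days from the second DLT to the end of evaluation of the first three, where the exception did not fire.

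| Spacing | Exception fires | Days left open |
|---|---|---|
| 1 day | 0.1% | 9 |
| 7 days | 5–6% | 8.5 |
| 14 days | 21–25% | 6 |
| 20 days | 31–36% | 4 |
| 28 days | 43–50% | 0 |

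If enrolment to that dose simply continued at the same pace, the open period would admit roughly 4/20 = 0.2 subjects per such cohort at 20-day spacing and 8.5/7 ≈ 1.2 at 7-day spacing. If enrolment closes at three, it admits none. A non-evaluable third subject would lengthen the period.

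**The case against.** Real controls exist. DLTs reach the Sponsor in real time, safety review meetings decide on enrolment, and the Sponsor assigns every dose (Section 3.2.1.1). Subjects are hospitalised from Cycle 0 Day 2 to Cycle 2 Day 2, with leave possible from Cycle 1 Day 8 (Section 6.1). A higher dose cannot open until three subjects complete evaluation. Nothing forbids an earlier rerun. All this stands, and it limits the harm. But these controls permit a pause without requiring one, and the protocol evidently thought a mandatory rerun necessary in the neighbouring case.

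Four stronger readings are tempting and not supported:
- **The plan requires replacement at the same dose.** The documents contain no replacement rule. The three-subject condition can be met by enrolling another subject, but no instruction says so. The third subject in the exception might also mean the third evaluable one, which would cover this case. The wording is ambiguous, and that reading would not cover expansion.
- **The plan breaches its own overdose control.** Section 11.11.3 applies the limit to the dose recommended for the next cohort, not continuously within a cohort. This is a gap between two rules, not a violation.
- **Two DLTs always exceed the limit.** The table shows that this depends on the denominator.
- **Planned accrual shows that subjects will be exposed.** It shows that the exception often does not fire. A new exposure also needs a fourth enrolment during the open period, which the documents neither schedule nor rule out.

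**Conclusion.** The point holds in limited form and should be fixed. Once three subjects are enrolled, a second DLT in the current cohort triggers no mandatory rerun before another subject joins that dose. Under the stated model, the dose would fail the 0.25 limit at every listed level for 2/2 and 2/3, whether lower doses are at 0/3 or 0/6. For 2/4 this holds at every level only with 0/3 below. Under the timing assumptions, the exception misses about two thirds of cohorts with two or more DLTs in the first three at planned average accrual, and nearly all at weekly spacing or closer.

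The exposure is extra subjects at the same dose, not escalation. It normally ends when the third subject completes evaluation, at most 28 days after that subject starts, and averages about 4 to 9 days at spacings of 1 to 20 days. The number of subjects affected cannot be fixed from the documents.

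**What to change.** Reconcile the exception in Section 3.2.1.2 with the constraint in Section 11.11.3 by deleting the condition about the third subject's enrolment. The revised rule would say that, once two subjects in the current cohort have had a DLT, the BLRM is re-evaluated with all available DLT outcomes before any additional subject is enrolled at that dose level, including by cohort expansion or to make up evaluable numbers. Enrolment then follows the updated model, so counts the model accepts, such as 2/9, are not blocked.

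The change is one sentence and uses the existing model, with no extra subjects or procedures. The cost is a short enrolment pause. Because pending subjects stay excluded, the first rerun will often be at 2/2, and its recommendation may change once the third subject finishes.
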